For subjects receiving rituximab subcutaneously, rituximab will be administered at a dose of 375 mg/m² via IV infusion on Cycle 1 Day 1. Subcutaneous rituximab hyaluronidase will be administered as 1,400 mg rituximab and 23,400 Units hyaluronidase per 11.7 ml total volume (120 mg/2,000 Units per mL) on Cycle 1 Days 8, 15, and 22 and on Day 1 of Cycles 3 through 6, for a total of 8 doses of rituximab in 6 cycles (7 doses of SC rituximab after the initial IV infusion). Rituximab will be procured by the clinical sites from commercial sources.

Name of Investigational Product: Tazemetostat (EPZ-6438)

Name of Active Ingredient: Tazemetostat

Sample Size Justification:

The primary objective of this study is to evaluate the overall response rate obtained in subjects with R/R FL, treated with the combination of rituximab and tazemetostat. Given the historical data with single agent rituximab (McLaughlin, 1998; Leonard, 2019), the Sponsor would consider the combined regimen to be of no further interest if the ORR were 50% or less, but of considerable interest if the ORR were at least 70%.

Simon's two-stage design (Simon, 1989) will be used. The null hypothesis that the true response rate is 50% will be tested against the one-sided alternative. In the first stage, 15 subjects will be accrued. If there are 8 or fewer responses in these 15 subjects, the regimen will be considered as futile.

Subject enrollment will continue during futility analysis. If 9 responses or greater (CR + PR) are seen in the initial 15 subjects, additional subjects will be accrued for a total of 54 evaluable subjects. The Sponsor expects 80% of enrolled subjects to have WT EZH2 status. Consequently, the study will enroll approximately 43 WT subjects as well as approximately 11 MT subjects. With an estimated early dropout rate of 10%, this study estimates a total accrual of 59 subjects.

For the primary analysis, the null hypothesis will be rejected if 27 or more responses (CR + PR) are observed in the first 43 evaluable subjects regardless of mutation status. This design yields a one-sided type I error rate of 0.05 and power of 0.801 when the true response rate is 70%.

If the primary analysis is successful, full set analysis will be conducted once 54 evaluable subjects are available regardless of mutation status. Subjects in the Full Analysis Set (FAS) will be stratified to 2 subgroups depending on their EZH2 mutation status (WT vs MT).

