With an estimated 54 eligible subjects in the combined FAS, rates of individual AEs can be estimated to within at most \pm 14% (95% confidence interval). Any AE with a true rate of at least 5% is likely to be observed at least once (93% chance).

Assuming accrual takes place over 24 months, with at least an additional 12 months of follow-up for progression, there would be approximately 65% power to rule out a benchmark median PFS of 12 months against the alternative of a true PFS of 18 months (one-sided, 0.05 level test) in the primary analysis subset of approximately 43 subjects with at least 26 PFS events. If PFS is similar in both subsets regardless of EZH2 status, then there would be 80% power for the same analysis in the combined FAS of approximately 54 subjects with at least 33 PFS events.

The reporting of response rate in the MT EZH2 subset (anticipated to be 11 subjects) will have very little precision and is exploratory only. Note, the subjects with MT EZH2 will be included in all safety analyses. Sample and power calculations are based on nQuery 8.0.

Number of Subjects (planned):

Approximately 59 subjects (assuming a 10% early drop-out rate resulting in approximately 54 evaluable subjects)

- Approximately 43 evaluable subjects with WT EZH2 (primary study population) and
- Approximately 11 evaluable subjects with MT EZH2

Diagnosis and Main Criteria for Eligibility

Inclusion Criteria:

- 1. Men and women of 18 years of age and older
- 2. Voluntary agreement to provide written informed consent and the willingness and ability to comply with all aspects of the protocol
- 3. Eastern Cooperative Oncology Group (ECOG) performance status of 0, 1, or 2 (Appendix 1)
- 4. Life expectancy (in the opinion of the Investigator) of ≥3 months before enrollment
- 5. Have histologically confirmed FL, Grades 1 to 3a. Subjects may have R/R disease following at least 2 standard prior systemic treatment regimens where at least 1 anti-CD20-based regimen was used
- 6. Treatment recommended in accordance with the Groupe d'Etude des Lymphomes Folliculaires (GELF) criteria due to the presence of at least one of the following:

Name of Investigational Product: Tazemetostat (EPZ-6438)

Name of Active Ingredient: Tazemetostat

- a. Any nodal or extranodal tumor mass >7 cm diameter
- b. Involvement of at least 3 nodal sites, each with diameter >3 cm
- c. Presence of any systemic or B symptoms
- d. Splenic enlargement with inferior margin below the umbilical line

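### The exact power of the written two-stage rule at a true ORR of 70% is 0.804, not the stated 0.801; the stated type I error of 0.05 is right.

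*Protocol*

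**What the plan says.** The Sample Size Justification in the protocol synopsis gives every input to the calculation.

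- Design: "Simon's two-stage design (Simon, 1989) will be used".
- Null rate: "The null hypothesis that the true response rate is 50% will be tested against the one-sided alternative".
- Target rate: the regimen would be "of considerable interest if the ORR were at least 70"%.
- Size of the first stage: "In the first stage, 15 subjects will be accrued".
- Futility boundary at that stage: "If there are 8 or fewer responses in these 15 subjects, the regimen will be considered as futile". With 9 or more responses the trial goes on.
- Final rule: "the null hypothesis will be rejected if 27 or more responses (CR + PR) are observed in the first 43 evaluable subjects regardless of mutation status".
- Claimed properties: "This design yields a one-sided type I error rate of 0.05 and power of 0.801 when the true response rate is 70"%.
- Software: "Sample and power calculations are based on nQuery 8.0".

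Protocol section 14.6 and SAP section 3.2.1 carry the same rule and the same two figures. SAP section 3.2.1 refers to its Appendix 1 for the calculation, but that appendix is blacked out in the public version.

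**The concern.** A two-stage rule with fixed stage sizes and boundaries has one exact power at a given response rate. All the inputs are printed, so the figure can be checked without further assumptions about the design. The plan gives power to three decimals, and the third decimal does not come out as printed.

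This is the power of the primary decision and it appears in three places. A wrong value could mean only that a digit is wrong. It could also mean that a boundary or stage size was mis-transcribed, which would be serious. The check has to tell these apart.

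**Working it through.** **Inputs** (protocol synopsis, repeated in protocol 14.6 and SAP 3.2.1): p0 = 0.50; p1 = 0.70; first stage n1 = 15, stop if 8 or fewer respond; total n = 43, so 43 − 15 = 28 in the second stage; reject if 27 or more respond in all.

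**Formula.** With X1 the first-stage and X2 the second-stage responses,

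P(reject | p) = Σ over x = 9 to 15 of P(X1 = x | 15, p) × P(X2 ≥ 27 − x | 28, p).

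**Power, p = 0.70**

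| x | P(X1 = x) | needed in stage 2 | P(X2 ≥ needed) | product |
|---|---|---|---|---|
| 9 | 0.14724 | 18 | 0.80867 | 0.11907 |
| 10 | 0.20613 | 17 | 0.89717 | 0.18493 |
| 11 | 0.21862 | 16 | 0.95090 | 0.20789 |
| 12 | 0.17004 | 15 | 0.97924 | 0.16651 |
| 13 | 0.09156 | 14 | 0.99225 | 0.09085 |
| 14 | 0.03052 | 13 | 0.99746 | 0.03044 |
| 15 | 0.00475 | 12 | 0.99927 | 0.00474 |

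The products sum to 0.80443, or 0.804. The stated figure is 0.801. The gap is 0.8044 − 0.8010 = 0.0034.

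**Type I error, p = 0.50.** The same sum gives 0.04993. To the two decimals stated this is 0.05, so the plan's figure is reproduced.

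**Is the rule itself sound?** A search over two-stage designs with total size 30 to 55, type I error at most 0.05 and power at least 0.80 at 50% versus 70% returns this rule (8 of 15, then 26 of 43 as the largest non-rejecting count) as the one with the smallest expected sample size under the null, 23.5. It is the Simon optimal design for the plan's own hypotheses, which argues against a mis-transcribed boundary or stage size.

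**Can another reading give 0.801?**

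| Reading | Type I error | Power |
|---|---|---|
| As written | 0.0499 | 0.804 |
| Single stage, reject at 27 or more of 43 | 0.063 | 0.883 |
| Single stage, reject at 28 or more of 43 | 0.033 | 0.808 |
| Two-stage after 8 of 15, reject at 28 or more of 43 | 0.028 | 0.750 |

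None does, and the alternatives also lose the match to a type I error of 0.05.

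**The case against.** The strongest reply is that the point is trivial. The figure agrees with the exact value to within 0.34 of a percentage point, it errs on the safe side, and the design meets its 5% and 80% targets. According to SAP sections 5.2, 8 and 9, the trial ended with 5 treated subjects and no futility or efficacy analysis will be done, so the 27 of 43 rule will never be used. All of that stands and fixes the weight of the point. It does not make 0.801 correct: the plan chose three decimals, and at three decimals the answer is 0.804.

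Three stronger readings are tempting, and the documents support none of them.

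- A reader might infer that the rule and its operating characteristics do not belong together. They do: the type I error matches, the power exceeds 80%, and the rule is the optimal design for the stated hypotheses. Only the last digit of the power is off.
- A reader might infer that 0.801 was taken from the Simon minimax design for the same hypotheses (stop at 12 or fewer of 23, reject at 24 or more of 37), which has type I error 0.0482 and power 0.8011. That is a guess. Other designs round to the same pair of figures: stopping at 11 or fewer of 19 and rejecting at 32 or more of 53 gives 0.0499 and 0.8012. A slip of one digit would explain 0.801 as well. The appendix that might settle it is redacted.
- A reader might go on to compare the chance of stopping at stage 1 under the two designs. That sets the trial's rule against a design the documents never mention, so it does not measure the effect of the wrong digit. Nor can it be said that the plan omits stopping probabilities, since they may be in the redacted appendix.

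**Conclusion.** The point holds as an editorial correction. The written rule has power 0.804 at a true ORR of 70%, against the stated 0.801. The error is 0.0034 and conservative. The stated type I error of 0.05 is correct for this rule (exact 0.0499). No boundary, stage size, sample size or decision is affected.

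The calculation assumes independent subjects with a common response rate, a futility rule that is obeyed, and first-stage responses that count unchanged towards the 43. These are the usual assumptions for a Simon design. If the futility rule were ignored, the single-stage figures in the working for rejection at 27 or more would apply, and those are further from 0.801. How 0.801 arose cannot be determined from the public documents.

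**What to change.** In the protocol synopsis (Sample Size Justification), protocol section 14.6 and SAP section 3.2.1, change the stated power from 0.801 to 0.804. Leave the type I error at 0.05. Whoever makes the edit can confirm the value against the nQuery output.

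The cost is one digit in three places. Nothing changes for subjects, procedures, boundaries or analyses. If the documents are not to be reissued after the early termination, it is enough to give the correct figure wherever the synoptic clinical study report restates the design.

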The first stage will enroll 15 subjects regardless of EZH2 mutational status. If there are 8 or fewer responses in these 15 subjects, the study will be considered futile. Enrollment will continue during the interim futility analysis. If 9 responses or greater are seen in the initial 15 subjects, additional subjects will be accrued for a total of 54 evaluable subjects regardless of mutation status. Futility analysis will be performed when the Cycle 6 Day 1 tumor assessment data are available for the first 15 subjects.

Based on Simon's 2-stage design, the primary analysis will occur after 43 evaluable subjects regardless of mutation status are available. Enrollment will continue during the primary analysis. Full set analysis will occur once data from 54 evaluable subjects regardless of mutation status are available.

Methodology:

This study includes a 28-day screening period, a 2-year (24-cycle) treatment period, and a follow-up period. During the treatment period, subjects will receive tazemetostat in combination with rituximab in 28-day cycles for the first 6 cycles followed by tazemetostat alone in 28-day cycles for the remaining 18 cycles, or until disease progression, unacceptable toxicity, or withdrawal of consent. Disease assessments will be performed at screening, Cycle 3 Day 1, Cycle 6 Day 1, Cycle 12 Day 1, Cycle 18 Day 1, and Cycle 24 Day 1.

Tazemetostat 800 mg twice daily will be administered daily starting on Cycle 1 Day 1 (C1D1). Tazemetostat is supplied by Epizyme in pre-counted, appropriately labeled bottles. Tazemetostat will be administered from C1D1 to the end of Cycle 24, for 24 months of therapy or until disease progression, unacceptable toxicity, or withdrawal of consent.

Rituximab will be administered by either subcutaneous injection or IV infusion according to the regional product prescribing information, labeling, and institutional guidelines. For subjects receiving rituximab via IV infusion, rituximab will be administered at a dose of 375 mg/m² on Day 1, 8, 15, and 22 of Cycle 1, and then on Day 1 of Cycles 3 through 6, accounting for an additional 4 doses (ie, a total of 8 doses of rituximab in 6 cycles).

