 - Note: Patients who are positive for HCV antibody must be negative for HCV-RNA by PCR to be eligible for study participation.
- 12. Females of childbearing potential (FCBP) must have a negative serum pregnancy test (beta-human chorionic gonadotropin [β-hCG] test with a minimum sensitivity of 25 mIU/mL or equivalent units of β-hCG) at screening and within 24 hours prior to the first dose of study drug. All females will be considered to be of childbearing potential unless they are naturally postmenopausal (at least 12 months consecutively amenorrhoeic [amenorrhea following cancer therapy does not rule out childbearing potential] and without other known or suspected cause) or have been sterilized surgically (ie, total hysterectomy and/or bilateral oophorectomy, with surgery completed at least 28 days prior to the first

Name of Investigational Product: Tazemetostat (EPZ-6438)

Name of Active Ingredient: Tazemetostat

dose of study drug).

- 13. FCBP must either practice complete abstinence or agree to use a highly effective method of contraception beginning at least 28 days prior to the first dose of study drug, during study treatment (including during dose interruptions), for 6 months after tazemetostat discontinuation, and for 12 months after rituximab discontinuation. If the contraception methods provided in Section 9.3 are not appropriate for the FCBP, she must be referred to a qualified contraception provider to determine the medically effective contraception method appropriate for the subject. Examples of highly effective methods of contraception (result in a failure rate of <1% per year when used consistently and correctly) may be found in Section 9.3. Female subjects must also refrain from breastfeeding or donating oocytes during study treatment and for 12 months following the last dose of rituximab.
- 14. Male subjects must have had a successful vasectomy (with medically confirmed azoospermia) OR must either practice complete abstinence or agree to use a latex or synthetic condom during sexual contact with a FCBP from the first dose of study drug, during study treatment (including during dose interruptions), and for 3 months after study drug discontinuation.

NOTE: Male subjects must not donate sperm from the first dose of study drug, during study treatment (including during dose interruptions), and for 3 months after study drug discontinuation.

Exclusion Criteria:

- 1. Prior exposure to tazemetostat or other inhibitor(s) of EZH2

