7.4.2. Dose Adjustment for Rituximab

The dose of rituximab should not be reduced. Administration of rituximab may be interrupted and modified according to the clinical practice of the Investigator's institution (eg, dose splitting or dose banding), and in line with the approved prescribing information including administration, warnings, precautions, contraindications, and adverse reactions, as applicable. In case a dose of rituximab is missed during Cycle 1 because of toxicity, it will not be rescheduled. In case of delay in the start of the next cycle (Cycles 3 through 6) due to toxicity, rituximab administration will be postponed until AE has resolved, at which point the next cycle is started. If rituximab is discontinued due to toxicity, tazemetostat should be continued as per protocol and the subject should continue in the study.

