- 13. FCBP must either practice complete abstinence or agree to use a highly effective method of contraception beginning at least 28 days prior to the first dose of study drug, during study treatment (including during dose interruptions), for 6 months after tazemetostat discontinuation, and for 12 months after rituximab discontinuation. If the contraception methods provided in Section 9.3 are not appropriate for the FCBP, she must be referred to a qualified contraception provider to determine the medically effective contraception method appropriate for the subject. Examples of highly effective methods of contraception (result in a failure rate of <1% per year when used consistently and correctly) may be found in Section 9.3 . Female subjects must also refrain from

Protocol EZH-1401 Amendment 2.0 21 October 2021

breastfeeding or donating oocytes during study treatment and for 12 months following the last dose of rituximab.

14. Male subjects must have had a successful vasectomy (with medically confirmed azoospermia) OR must either practice complete abstinence or agree to use a latex or synthetic condom during sexual contact with a FCBP from the first dose of study drug, during study treatment (including during dose interruptions), and for 3 months after study drug discontinuation.

NOTE: Male subjects must not donate sperm from the first dose of study drug, during study treatment (including during dose interruptions), and for 3 months after study drug discontinuation.

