9.3.3. Pregnancy Prevention

9.3.3.1. Female Subjects

FCBP must either practice complete abstinence or agree to use a highly effective method of contraception beginning at least 28 days prior to the first dose of study drug, during study treatment (including during dose interruptions), for 6 months after tazemetostat discontinuation, and for 12 months after rituximab discontinuation. Female subjects must also not breastfeed or donate oocytes during study treatment and for 12 months following the last dose of rituximab. If the below contraception methods are not appropriate for the FCBP, she must be referred to a qualified contraception provider to determine the medically effective contraception method appropriate for the subject. The following are examples of highly effective methods of contraception (result in a failure rate of <1% per year when used consistently and correctly):

• Intrauterine device (IUD)

- Intrauterine hormone-releasing system (IUS)
- Hormonal (ovulation inhibitory combined [estrogen and progesterone]: oral, intravaginal, or transdermal; ovulation inhibitory progesterone-only: oral, injectable, or implantable)

NOTE: Due to the potential of enzyme induction with tazemetostat, hormonal contraception methods must be supplemented with a barrier method of contraception (preferably male condom)

- Bilateral tubal ligation
- Partner's vasectomy (if medically confirmed [azoospermia] and sole sexual partner)

NOTE: Female subjects of childbearing potential exempt from these contraception requirements are subjects who practice complete abstinence from heterosexual sexual contact. True abstinence is acceptable when this is in line with the preferred and usual lifestyle of the subject. Periodic abstinence (e.g., calendar, ovulation, symptothermal, or post ovulation methods) and withdrawal are not acceptable methods of contraception.

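### The post-treatment ban on oocyte donation runs only from the last rituximab dose, so a woman who completes 24 cycles of tazemetostat has no donation restriction after her last tazemetostat dose

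*Protocol*

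**What the plan says.** The donation rule appears three times in the protocol. Synopsis inclusion criterion 13 reads "Female subjects must also refrain from breastfeeding or donating oocytes during study treatment and for 12 months following the last dose of rituximab". Section 8.1.1 has the same text ("breastfeeding or donating oocytes during study treatment and for 12 months following the last dose of rituximab"), and Section 9.3.3.1 says "Female subjects must also not breastfeed or donate oocytes during study treatment and for 12 months following the last dose of rituximab". None of the three adds a period counted from tazemetostat.

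Two neighbouring rules do count from tazemetostat:

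- The contraception sentence in criterion 13 applies "for 6 months after tazemetostat discontinuation, and for 12 months after rituximab discontinuation".
- The note to criterion 14 says "Male subjects must not donate sperm from the first dose of study drug, during study treatment (including during dose interruptions), and for 3 months", counted from the end of study drug. Section 9.2.5 glosses study drug as tazemetostat.

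On dosing, rituximab is given four times in Cycle 1 "and then on Day 1 of Cycles 3 through 6, accounting for an additional 4 doses". For tazemetostat, the synopsis says "Tazemetostat will be administered from C1D1 to the end of Cycle 24". Cycles last 28 days. Section 7.4.2 lets the two drugs separate earlier: "If rituximab is discontinued due to toxicity, tazemetostat should be continued as per protocol and the subject should continue in the study".

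**The concern.** The rule is anchored to the drug that is planned to stop first. During dosing the ban holds, because time on tazemetostat is study treatment. Once tazemetostat stops, the only restriction left is whatever remains of the rituximab window, and for a woman treated as planned nothing remains.

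A subject's own contraception protects against her own pregnancy. It does nothing for the recipient of a donated oocyte, and the protocol has a separate donation sentence. Section 9.3 attributes a potential teratogenic risk to tazemetostat. It speaks of pregnancies conceived during exposure, which the in-treatment ban already addresses. The argument for a post-treatment period therefore rests on the protocol's own 6-month contraception rule, which implies some residual risk after the last dose.

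Breastfeeding sits in the same sentence but matters less. Lactating women are excluded, pregnancy is tested on Day 1 of each cycle, and contraception continues for 6 months after tazemetostat.

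**Working it through.** The plan states no figure for this point, so there is none to reproduce. The check is calendar arithmetic.

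**Inputs.** From the protocol synopsis: 28-day cycles; rituximab on Days 1, 8, 15 and 22 of Cycle 1 and Day 1 of Cycles 3 to 6; tazemetostat to the end of Cycle 24. Assumptions: no dose delays; 12 months = 365 days, 6 months = 183 days, 3 months = 91 days.

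**Formula.** Study day = (cycle − 1) × 28 + day of cycle. The rituximab days are 1, 8, 15, 22, 57, 85, 113 and 141. That is 8 doses, which matches the stated total.

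**End of the rituximab window.** Cycle 6 Day 1 = 5 × 28 + 1 = Day 141, and 141 + 365 = Day 506 (Cycle 19 Day 2). A ±3-day visit window on the last dose gives Days 503 to 509.

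**End of planned tazemetostat.** 24 × 28 = Day 672, which is 672 − 506 = 166 days after the window has closed.

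**Days of donation ban left when tazemetostat stops** (506 − stop day, not below zero):

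| Tazemetostat stops | Study day | Days left |
|---|---|---|
| End of Cycle 12 | 336 | 506 − 336 = 170 |
| End of Cycle 18 | 504 | 506 − 504 = 2 |
| Day 506 or later | ≥ 506 | 0 |
| End of Cycle 24 | 672 | 0 |

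**Against the protocol's own neighbouring periods.** These are comparators, not a stated donation requirement. Cover falls below the 6-month contraception period for stops after 506 − 183 = Day 323 (Cycle 12). It falls below the men's 3 months for stops after 506 − 91 = Day 415 (Cycle 15).

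**Early rituximab stop with tazemetostat continuing.** If the last rituximab dose is Cycle 1 Day 22, the window closes on 22 + 365 = Day 387, and cover drops below 6 months for stops after 387 − 183 = Day 204. If only the Day 1 dose is given, these days are 366 and 183. This matters only for women who stop tazemetostat before Day 506; a completer has zero in every case.

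**Treatment beyond 24 cycles.** Footnote c of Table 2 allows it. It does not enlarge the gap, because dosing time is itself covered.

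**Could another section close the gap?** Section 12.4.2 deals with pregnancy and with exposure through breastfeeding, mainly within 30 days of the last dose. It sets reporting duties and restricts nothing.

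**The case against.** The strongest objection is that a contraception period does not transfer automatically to donation. The tazemetostat reproductive finding in Section 9.3 is skeletal abnormality in fetuses of pregnant rats. Contraception after treatment protects a fetus carried by a woman who may still have drug in her body, whereas the recipient of an oocyte has not taken the drug. The documents give no oocyte-specific or gamete-specific data. This stands as a limit on how much protection can be said to be missing. It does not remove the inconsistency: the protocol bans oocyte donation during treatment and sperm donation for 3 months after study drug, so it already treats gamete donation as a concern. A male completer keeps a restriction and a female completer does not, with no reason given.

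A second objection is that 6 months is a choice, since the other donation rule uses 3. That is fair. The documents state no length, so the sponsor should be free to justify another.

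A third is reach. Section 5.1 gives an average age at diagnosis of 65, and an affected woman would have to stay on tazemetostat for a long time and then donate. SAP Section 5.2 reports early termination with 5 treated patients. This limits the severity but does not make the text right. The consent form and the Investigator Brochure were not available and may carry donation instructions.

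**Conclusion.** The concern holds, as a minor one. Followed as written, the rule leaves a woman who stops tazemetostat on or after about Day 506 with zero days of oocyte-donation restriction after that drug. This is the outcome for anyone who completes the planned 24 cycles. Women who stop between about Day 323 and Day 506 keep some cover, but less than 6 months.

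The day counts assume on-schedule dosing and move with visit windows, postponed rituximab or early rituximab discontinuation. The result for a completer is zero without delays and in both early-stop cases.

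The gap concerns donation and, secondarily, breastfeeding; contraception still applies for 6 months after tazemetostat. At most 5 treated patients could be affected, possibly none. Sample size, error rates and analyses are untouched.

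**What to change.** In criterion 13 (synopsis and Section 8.1.1) and in Section 9.3.3.1, keep the in-treatment ban and the 12 months from the last rituximab dose, and add 6 months counted from stopping tazemetostat. This matches the contraception sentence beside it. If the sponsor prefers another length, it should state it and give the reason. With 6 months, a completer's ban would run to about Day 855 (672 + 183).

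The cost is one clause in three places, with no extra visit or test. The consent form should be aligned if it carries the same wording. As the study has ended, the remaining steps are to check whether any of the 5 treated patients is a woman to whom this applies, and to correct the sentence wherever it is reused.
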